**Low Intensity Focused Ultrasound of Medial Temporal Lobe
Regions for the Improvement of Learning and Memory /
Low Intensity Focused Ultrasound as a Non-Invasive Neural
Prosthetic for the Improvement of Emotion Regulation**

NCT03717922
Document Date: 12/8/2023

APPROACH

Participants. Participants will consist of 21 adults aged 35-90

Subject Recruitment. Participants will be recruited from the Human Connectome Project – Aging participant pool and through fliers placed around campus and greater Los Angeles.

Eligibility. Inclusion criteria: 1) age 35-90, 2) right handed, 3) English dominant language.

Exclusion criteria: contraindications for MRI (e.g. metal implants, pregnancy), history of head injury sufficient to warrant medical attention, history of alcohol or substance abuse or dependence, history of major psychiatric illness requiring treatment, history of cancer or other neoplastic syndromes, history of major neurologic illness (e.g. epilepsy).

Procedures.

Crossover Design. This study will be conducted using a crossover design in which each participant will complete two visits spaced two weeks apart. At one visit, they will receive LIFUP sonication to the right amygdala, and at the other, they will receive sonication to the left entorhinal cortex. The order of conditions will be randomized and counterbalanced across participants. Participants will be blinded to condition order, and all other testing will be conducted the same at both visits.

Screening. Participants who have consented to be contacted regarding future research projects will be contacted by study staff who will conduct a telephone screening to ensure eligibility.

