fMRI and LIFUP administration. Prior to receiving LIFUP sonication, the LIFUP transducer will be aimed at the appropriate target region for the visit (either the amygdala or the entorhinal cortex) and gently strapped in place to their head. Participants will then return to the scanner where a T1 image will verify the position of the LIFUP transducer and allow for estimation of the spatial location of the sonication beam focus. If needed, adjustments to transducer placement will be made to ensure that the beam focus is correctly aimed; an additional T1 will be collected after adjustment. Once correct placement of the transducer has been confirmed, LIFUP will be administered in 10 sonifications at 650kHz, 720mW/cm, duty cycle 5% duration 30s, with 30s spacing between sonifications. LIFUP will be administered with a pulse repetition frequency of 10Hz for amygdala sonication and 100Hz for entorhinal cortex sonication. BOLD fMRI will be collected simultaneously during LIFUP administration.

MRI Data Acquisition. We will use a 3-Tesla Siemens PRISMA scanner. We will collect T1, T2, hi-res hippocampal T2, and diffusion-weighted structural images for each participant.

Additionally, we will collect arterial spin labeling and BOLD fMRI both before and after LIFUP, as well as BOLD fMRI during LIFUP administration. We will be using Human Connectome Project scan sequences to collect these images; detailed information about the protocols can be obtained here: <http://www.humanconnectome.org/documentation/Q1/imaging-protocols.html>.

Behavioral Testing. Participants will be administered the behavioral tests described below twice at each of their in-person sessions; once before LIFUP and once after LIFUP.

Verbal Free Recall Task. Verbal memory will be assessed using the Rey Auditory Verbal Learning Test (RAVLT) which involves repeated presentation of a list of 15 words. The order of RAVLT form administration will be randomized and counterbalanced across participants.

Spatial Navigation Memory Task. Participants will be presented with a computerized spatial arena simulating a museum art gallery. They will be instructed to learn the locations of three objects placed throughout the gallery. After the Learning Phase, the subjects will then be asked to locate the objects' shown location sans stimuli immediately after learning the set of locations of each object. After each learning phase, participants will complete an unrelated Distractor Task

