within the task but unrelated to the Mission. The navigation and distractor task paradigm will be repeated three times. During the fourth and final trial, retrieval of spatial information during this trial will be measured as the distance between the location that participants selected and the true location of the object. Shorter distances will indicate better spatial memory performance. This assessment has four forms, the order of which will be randomized and counterbalanced across participants.

Brief Visuospatial Memory Test. In this test, the participant is presented with a 2x3 array of geometric figures for 10 seconds, then instructed to draw the figures from memory in the correct location on the page. The task consists of three learning trials, one long delayed recall trial, and one recognition trial. Learning performance will be calculated as the proportion of presented figures and figure locations successfully recalled during the initial presentations of the six-figure array. Long delayed recall memory performance will be calculated as the proportion of presented figures and figure locations successfully recalled freely after a 20-minute delay. Memory retention will be calculated as the proportion of presented figures successfully identified during a forced-choice recognition task. This assessment has 4 forms that will be used for repeat testing, the order of which will be randomized and counterbalanced across participants.

State Trait Anxiety Inventory. This is a questionnaire used to measure anxiety-like symptoms. The first half of the questionnaire asks about the degree to which several listed statements align with how a participant feel at the current moment (state anxiety). The second half asks about the degree to which the listed statements align with how a participant typically feels (trait anxiety).

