International Affective Picture Stimuli Task. In this task, participants complete multiple trials in which a 15-second fixation cross is followed by a 2-second color-coded instruction for one of three trial types: WATCH (passively view a negative image), VIEW (passively view a neutral image), or REAPPRAISE (actively reappraise a negative image). The instruction image is followed by a 5 second presentation of a negatively or neutrally-valenced image. After each image presentation, participants rate their subjective level of current arousal and the degree of awfulness of the image (valence). The task consists of 24 VIEW trials, 24 WATCH trials, and 48 REAPPRAISE trials. Objective reactivity to each stimulus will be measured using galvanic skin response and heart rate. Emotional reactivity in this task will be quantified using the difference between negative and neutral stimuli (N-S). Emotional reappraisal will be quantified by taking the difference of the negative reappraisal stimuli and the negative stimuli (NR - N).

Data Analysis Plan.

Hypothesis 1a. LIFUP of the amygdala will decrease BOLD activation in the amygdala and functionally associated regions (e.g. DLPFC), as well as functional connectivity between the amygdala and connected regions. It will also increase perfusion in the amygdala. These changes will not be observed in response to LIFUP of the entorhinal cortex.

Hypothesis 1b. LIFUP of the entorhinal cortex will increase BOLD activation in the entorhinal cortex and functionally associated regions (e.g. DLPFC), as well as functional connectivity between the entorhinal cortex and connected regions. It will also increase perfusion in the entorhinal cortex. These changes will not be observed in response to LIFUP of the amygdala.

MRI Analysis. Analyses will be performed using FSL Version 5.0 (www.fmrib.ox.ac.uk/fsl). Stimulation-related functional data processing will include motion correction to the mean image, spatial smoothing (Gaussian Kernel FWHM = 8mm), high-pass temporal filtering ($t > 0.01$ Hz) and regression-based removal of outliers. Processing of rs-fMRI will include correcting for

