RS-fMRI. We will compare the functional connectivity of the brain at rest before and after stimulation. Independent component analyses (ICA) will be used to statistically extract functional networks from each participant's rs-fMRI. Dual-regression analysis will then compare resting state networks between baseline and post-LIFUP to determine the effect of LIFUP on resting state functional connectivity. Age, sex and education will be included as additional regressors. Dual regression will also assess the association between these LIFUP-related longitudinal resting state network changes and emotional reactivity and memory performance.

Arterial Spin Labeling. Pulsed Arterial Spin Labeling (PASL) scans produce a perfusion image with voxel values representing local perfusion rates. For each subject, will be collected both before and after LIFUP. These PASL images will then be linearly registered to each subject's T1 structural image. Perfusion images will be processed by using the BASIL (Chappell et al., 2008) toolbox, including partial volume correction, then transferred to MNI space using non-linear registration in FSL. Then, a comparison of pre-vs-post tFUS sonication perfusion in the amygdala and entorhinal cortex will be conducted individually for each subject by subtracting the registered pre- sonication perfusion map from the post-sonication perfusion map. A 2×2 repeated measures analysis of variance (ANOVA), corrected for multiple comparisons using False Discovery Rate (FDR), will then be used to compare the longitudinal perfusion changes between amygdala sonication and ErC sonication.

Hypothesis 2. LIFUP of the amygdala will result in reduced subjective emotional reactivity to emotionally-salient stimuli compared to those presented before LIFUP; this reduction will not be observed with entorhinal cortex LIFUP.

Behavioral Analysis. Subjects, who will be unaware of the exact timing of the sonication onset, will be asked to report any unusual feelings, sensations or distress. To determine the effect of LIFUP on emotional reactivity, analyses of variance (ANOVA) will compare subjective valence

and arousal ratings between pre-LIFUP and post-LIFUP administrations of the IAPS task. Additionally, state and trait anxiety scores will be compared pre and post-LIFUP to determine LIFUP-related changes in anxiety levels.

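### The affective picture task is given four times with no rotated picture sets specified, and the Hypothesis 2 ratings test is written as pre versus post only, so repeat exposure is not separated from a LIFUP effect

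*Combined protocol and SAP*

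**What the plan says.** All references are to the combined protocol and SAP.

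- **Number of administrations.** Under Crossover Design, "each participant will complete two visits spaced two weeks apart". Under Behavioral Testing, the tests are given "twice at each of their in-person sessions; once before LIFUP and once after LIFUP".
- **Memory tests.** Verbal Free Recall Task: "The order of RAVLT form administration will be randomized and counterbalanced across participants". Spatial Navigation Memory Task: "This assessment has four forms, the order of which will be randomized and counterbalanced across participants". Brief Visuospatial Memory Test: "This assessment has 4 forms that will be used for repeat testing, the order of which will be randomized and counterbalanced across participants".
- **Picture task.** The International Affective Picture Stimuli Task section gives trial timing, three trial types, ratings, physiological measures and scoring, and states "The task consists of 24 VIEW trials, 24 WATCH trials, and 48 REAPPRAISE trials". It does not mention alternate picture sets, set order, or how pictures are assigned to administrations. Reactivity is scored as a negative-minus-neutral difference.
- **Hypothesis 2.** "LIFUP of the amygdala will result in reduced subjective emotional reactivity to emotionally-salient stimuli compared to those presented before LIFUP". The same sentence adds that entorhinal sonication will not show this reduction.
- **Analysis.** The Behavioral Analysis under Hypothesis 2 is an ANOVA of valence and arousal ratings, pre-LIFUP against post-LIFUP. Target is not named as a factor. The Physiological Analysis of the same task does list target, timepoint and instruction as factors, for interbeat intervals.

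**The concern.** The plan recognises the repeat-testing problem for three tasks and writes the same control into each. The fourth repeatedly given task, which supplies the ratings for Hypothesis 2, has no stated control.

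There are two possibilities, and each needs a written rule. If the same pictures return, responses may weaken with repetition, and a pre-to-post fall is what Hypothesis 2 predicts after amygdala sonication. If different pictures are used but their order is not rotated, a more or less evocative set always falls before or after LIFUP, and its content cannot be separated from the intervention; the direction of that bias is unknown.

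Either would matter less if the test compared the pre-to-post change between targets. As written, the ratings analysis compares pre with post, so a significant fall could be reported as support for Hypothesis 2 when it reflects only a second viewing.

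**Working it through.** The plan states no power, alpha, effect size or standard deviation for this endpoint, so there is no figure to reproduce. The two-sided 5% level, habituation sizes and correlations below are assumptions; n = 21 is from the Participants section.

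**1. Exposure.** 2 visits × 2 administrations = 4. Trials per administration: 24 + 24 + 48 = 96, of which 24 + 48 = 72 are negative. Over the study: 4 × 96 = 384 trials, 4 × 72 = 288 negative and 4 × 24 = 96 neutral.

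**2. Pre/post test with no LIFUP effect.** Let d be the fall from repetition in SDs of a single score, and r the pre/post correlation. The standardised mean change is dz = d / √(2(1 − r)). The paired t statistic is noncentral t with 20 degrees of freedom and noncentrality dz × √21; the two-sided 5% critical value is 2.086. For example, d = 0.3 and r = 0.6 give dz = 0.3 / √0.8 = 0.335, noncentrality 0.335 × 4.583 = 1.54, and rejection probability 31%.

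| Assumed fall d | dz at r = 0.6 | Rejects | dz at r = 0.8 | Rejects |
|---|---|---|---|---|
| 0.2 SD | 0.224 | 16% | 0.316 | 28% |
| 0.3 SD | 0.335 | 31% | 0.474 | 54% |
| 0.5 SD | 0.559 | 68% | 0.791 | 93% |

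**3. Comparison with the between-target contrast.** Here habituation is expressed in SDs of the change score and is equal at both visits. Figures are from 100,000 simulated trials per row, with 11 participants in one order and 10 in the other, and independent change scores at the two visits. The second to fourth columns count falls in the predicted direction only, so the nominal rate for a single test is 2.5%.

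| Habituation | Amygdala pre/post significant | Pre/post pooled over visits significant | Amygdala significant, entorhinal not | Target-by-time (two-sided) |
|---|---|---|---|---|
| 0 | 2.5% | 2.6% | 2.4% | 5.1% |
| 0.2 | 13.8% | 23.5% | 11.9% | 5.0% |
| 0.3 | 25.9% | 45.8% | 19.3% | 4.9% |
| 0.5 | 58.7% | 87.0% | 24.2% | 4.8% |

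The pre/post test is exposed whether run at the amygdala visit or pooled. Reading the specificity clause as two separate tests does not protect it either. The target-by-time contrast holds its level.

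**4. Unequal habituation.** If it is 0.5 at the first visit and 0.25 at the second, the contrast has a small expected bias because 21 is odd: (0.25 × 11 − 0.25 × 10) / 21 = 0.012. It rejected in 4.7% of simulated trials.

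**5. Effect of scoring.** On the negative-minus-neutral score, a fall common to both picture types cancels, and only the excess fall for negative pictures counts. If that excess were half the values in step 2 (0.1, 0.15, 0.25 SD), rejection at r = 0.6 would be 8%, 11% and 23%.

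**The case against.** **The plan is silent; it does not say that pictures recur.** This stands. A reader might infer that one fixed picture list is shown four times. The documents do not support that: the counts are of trials, and the Hypothesis 2 wording can be read as different stimuli before and after LIFUP. What can be said is that no sets are specified. It follows that bias toward Hypothesis 2 is conditional on reuse.

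**Habituation works against half of Hypothesis 2.** This also stands. A reader might infer that repetition alone can satisfy the whole hypothesis. Habituation would be expected at the entorhinal visit too, where no reduction is predicted, and target order is randomised and counterbalanced. The protection is real, however, only if the change is compared between targets, and the ratings ANOVA does not say so.

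**The inflation comes mainly from the analysis, not the pictures.** Largely correct: the target-by-time contrast stays near 5% in step 3 with no change to the stimuli. New pictures would also leave general task or session habituation in place. That is why picture sets alone are not a sufficient remedy. They still matter, because they remove picture-specific habituation and stop set content being tied to pre/post.

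**The difference score cancels common habituation.** True for that score, but the Hypothesis 2 analysis sentence refers to valence and arousal ratings without repeating the difference.

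**Physiology is already covered.** In part: the interbeat-interval model includes target and timepoint, although it does not name their interaction. Hypothesis 2 itself is worded for subjective reactivity.

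**Conclusion.** The concern holds in a conditional form. The task is given four times, no alternate or counterbalanced picture sets are specified for it although all three memory tests have them, and the Hypothesis 2 ratings test is written without target. Followed as written, that pre/post contrast cannot separate LIFUP from repeat exposure or, if unrotated sets are used, from set content.

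The rejection rates of 16% to 93% apply to a single pre/post test under assumed habituation of 0.2 to 0.5 SD and correlations of 0.6 to 0.8. The documents supply neither quantity, and the rates are lower for the negative-minus-neutral score. They should not be read as the error rate of a between-target analysis. The plan should be changed on both the stimuli and the test; clarifying the stimuli alone would leave the larger part of the problem.

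**What to change.** 1. **International Affective Picture Stimuli Task.** Specify picture sets matched on valence and arousal. Ideally use four, one per administration: 4 × 96 = 384 pictures, 288 negative and 96 neutral. If the pool is too small, use at least two, so that no picture repeats within a visit. Rotate set order across participants as is done for the memory forms.
2. **Behavioral Analysis under Hypothesis 2.** Name the target-by-time interaction (amygdala/entorhinal × pre/post) on the negative-minus-neutral score as the test, using the target and timepoint factors already in the physiological model, and include picture set as a factor.

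The first part removes picture-specific habituation only. The second handles general task habituation that is equal at both visits.

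**Cost.** Stimulus preparation before enrolment, and a change to one analysis paragraph. Whether a matched pool of 384 pictures is available cannot be told from the documents. Some set noise will remain: four rotations by two target orders make eight cells, and 21 / 8 = 2.6, so the cells cannot be equal.

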motion artifacts (using framewise displacement calculations, DVARS and within-subject independent component analysis), scrubbing, slice timing, unwarping and spatial smoothing (Gaussian Kernel FWHM = 8mm). Functional data will be linearly registered to stereotaxic MNI space and co-registered with anatomic data for each participant. Processing of diffusion imaging will include correction for motion, eddy distortion and susceptibility induced distortion and then fitting diffusion tensors to the data, Subjects with greater than 3mm mean displacement will be excluded from analyses. Structural data (T1 and DTI) will be linearly registered to the standard MNI152 T1 2mm brain.

Stimulation-related fMRI Analysis. BOLD fMRI will be collected continuously during the LIFUP paradigms. A block-design model will be used to statistically compare the BOLD signal during LIFUP stimulation blocks to the BOLD signal during no-stimulation blocks. To examine effect of stimulation to target ROI activity, we will extract average BOLD response rates in both the targeted and control (non-targeted) region for each of the blocks and use mixed-effect models to compare activity during LIFUP conditions (on / off) within each ROI. To examine LIFUP-related network connectivity, we will use a seed-based approach and examine whole brain connectivity with the LIFUP target of interest and compare between stimulation (on-off) conditions using psychophysiological interaction modeling (PPI). To assess changes in connectivity in relationship to LIFUP, we will use dynamic connectivity to evaluate changes in ROI across each LIFUP condition. Finally, dynamic causal modeling will allow us to assess and compare how changes in activation in the LIFUP target may causally affect activation in other regions (e.g. increased amygdala activation leads to increased DLPFC activity).

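### H1a, H1b and H2 predict no change under the other target, but the plan has only difference tests, so absence could be supported only by a non-significant result in 21 people

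*Combined protocol and SAP*

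**What the plan says.** Three hypotheses in the Data Analysis Plan pair a predicted effect with a predicted non-effect:

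- Hypothesis 1a, on amygdala sonication, adds of entorhinal sonication: "These changes will not be observed in response to LIFUP of the entorhinal cortex".
- Hypothesis 1b is the mirror image: "These changes will not be observed in response to LIFUP of the amygdala".
- Hypothesis 2, on subjective emotional reactivity, adds: "this reduction will not be observed with entorhinal cortex LIFUP".

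The analyses attached to them are:

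- **Regional BOLD** (Stimulation-related fMRI Analysis): extract the response in the targeted and the non-targeted region and "use mixed-effect models to compare activity during LIFUP conditions (on / off) within each ROI". No target-by-condition term is stated.
- **Perfusion** (Arterial Spin Labeling): a 2×2 repeated measures ANOVA to "compare the longitudinal perfusion changes between amygdala sonication and ErC sonication". This is a direct between-target comparison.
- **Ratings** (Behavioral Analysis under Hypothesis 2): ANOVA of valence and arousal before against after sonication. No target factor is stated.

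The Physiological Analysis section does include target as a factor, but its outcome is the interbeat interval, not the subjective ratings.

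On size and design, the Approach section says "Participants will consist of 21 adults aged 35-90" and "each participant will complete two visits spaced two weeks apart". There is no sham condition; each target is the other's control. The documents give no alpha, sidedness, power calculation, expected effect, SD, equivalence margin or rule for judging absence.

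**The concern.** A test for a difference can support the first half of each hypothesis but not the second. If the change under the other target is not significant, the data may mean that there is no change, or that 21 people were too few to see it. The plan offers no way to tell these apart.

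This matters because the two targets control each other, so the second halves carry the claim that an effect depends on where the beam is aimed. A moderate effect under the other target, from whatever cause, could be reported as no effect.

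For BOLD and the ratings there is a second gap. A significant result for one target beside a non-significant result for the other does not show that the two differ, and no contrast that would show it is stated.

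**Working it through.** There is no power figure in the documents to reproduce. The check asks how often a control-target test would miss a real change.

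**Inputs from the documents.** n = 21; each person receives both targets, so a before/after or on/off comparison within one target is paired. The MRI Analysis section excludes subjects with more than 3 mm mean displacement and does not say how many are expected, so the imaging n may be below 21.

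**Assumptions.** Alpha 0.05, two-sided or one-sided; true control-target change d = 0.5, in units of the SD of the within-person change; complete pairs.

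**Miss rate.** Power comes from the noncentral t distribution with n − 1 degrees of freedom and noncentrality d√n.

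- n = 21: noncentrality = 0.5 × √21 = 0.5 × 4.583 = 2.291, df = 20.
- Two-sided 0.05: critical value 2.086, power 58.7%, miss rate 41.3%.
- One-sided 0.05: critical value 1.725, power 71.5%, miss rate 28.5%.
- n = 18 (illustrating three exclusions): miss rate 48.4% two-sided, 34.8% one-sided.

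**Sensitivity at n = 21.**

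| Assumption varied | Miss rate |
|---|---|
| d = 0.3, two-sided 0.05 | 74.2% |
| d = 0.4, two-sided 0.05 | 58.5% |
| d = 0.6, two-sided 0.05 | 25.6% |
| d = 0.8, two-sided 0.05 | 6.4% |
| d = 0.5, two-sided 0.025 | 53.7% |
| d = 0.5, two-sided 0.01 | 68.2% |

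If 0.5 SD instead means the SD of the raw score, then d = 0.5/√(2(1 − ρ)), where ρ is the pre-post correlation. The two-sided miss rate is then 54.6% at ρ = 0.3, 41.3% at 0.5, 19.7% at 0.7 and 6.9% at 0.8.

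**What an interval could show.** The 95% CI half-width at n = 21 is about 2.086/4.583 = 0.46 SD of the change. If the true control-target change is zero:

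- A one-sided bound at 0.05 that excludes a change of 0.5 SD in the predicted direction succeeds 71.5% of the time (the same calculation as the one-sided test above). It reaches 80% at a margin of about 0.56 SD.
- A two-sided equivalence test (two one-sided tests at 0.05) with a margin of ±0.5 SD succeeds about 43% of the time. It reaches 80% at a margin of roughly 0.65 to 0.70 SD.

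**Significant here, not significant there.** If both targets truly produced the same 0.5 SD change and the two tests were independent, a significant amygdala result with a non-significant entorhinal result would occur in 0.587 × 0.413 = 24% of trials, although the targets do not differ.

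**Does a between-target contrast settle absence?** No. The perfusion ANOVA can show that the two changes differ. It cannot show that the smaller one is zero.

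**The case against.** The strongest reply has four parts.

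1. *The hypotheses predict; they do not conclude.* This stands. A reader might infer that the plan declares an effect absent whenever p > 0.05. No section says so. What can be said is that the plan gives no other criterion by which the prediction could be judged.

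2. *The trial does not claim full anatomical specificity.* This also stands. A reader might infer a claim that nothing but the sonicated region responds. Hypotheses 1a and 1b say otherwise: each predicts changes in associated regions, such as DLPFC, and in connectivity.

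3. *The predictions are directional.* This stands and changes the figures. Hypothesis 2 denies only a reduction. Hypothesis 1a predicts lower DLPFC activation under amygdala sonication, while 1b predicts higher DLPFC activation under entorhinal sonication, so 1a's second half is compatible with an opposite change. A two-sided equivalence margin does not fit such predictions, and it would be wrong to say that no margin below about 0.65 SD can be shown with 80% power: a one-sided bound manages about 0.56 SD.

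4. *The miss rate rests on values that the documents do not give, and perfusion already has a direct contrast.* Both are true. The 41% is conditional, and it applies to one test, not to a hypothesis made up of several outcomes. The perfusion ANOVA closes the between-target gap for that outcome, though not the absence gap.

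What the reply does not touch is that a non-significant result does not show absence at any alpha, and that the plan contains nothing else to show it.

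**Conclusion.** The point holds in limited form. All three hypotheses have a second half that predicts absence, all planned analyses test for a difference, and for regional BOLD and the Hypothesis 2 ratings not even a between-target contrast is stated. That follows from the text and needs no assumption.

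The size does need assumptions. For a paired test with 21 complete pairs and a true change of 0.5 SD of the within-person change, the miss rate is about 41% (two-sided 0.05) or 29% (one-sided 0.05). At that effect it runs from about 29% to 68% over the alpha levels and sidedness tried, is higher with fewer pairs, and is as low as 7% if the SD is that of the raw score and the pre-post correlation is 0.8.

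A reader might also infer that the weakness always favours the hypotheses, because noisier data make a null control result more likely. The documents do not support that in general: each hypothesis also needs the target effect to be detected, and noise works against that.

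**What to change.** 1. Restate the second half of Hypotheses 1a, 1b and 2 as a between-target difference in the predicted direction. Test it with a target-by-condition term for regional BOLD and a target-by-time term for the ratings. The perfusion ANOVA and the interbeat-interval model already allow this kind of comparison. The rewording needs the test: without it, the new claim would go untested for BOLD and the ratings.
2. For region-of-interest, perfusion and rating outcomes, report the control-target change with its 95% CI, and do not infer absence from p > 0.05. This rule is limited to outcomes with a single change score; whole-brain connectivity, dual regression and dynamic causal modeling do not yield one.
3. Claim absence only if the interval excludes a change as large as a margin fixed before analysis, in the predicted direction where the hypothesis is directional. Otherwise report absence as not established. State the alpha and sidedness used.

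**Cost.** Changes to three hypotheses, two added model terms and one reporting rule; no new participants or data. The claim becomes more modest. The contrast is not highly powered either: for true changes of 0.5 SD and 0 with equal SDs, its two-sided 0.05 power at n = 21 is about 34% if the two visits' changes are uncorrelated and 59% if they correlate at 0.5. The plan should say so.

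### BOLD data reach MNI space by a linear fit only, while perfusion in the same participants and regions is warped non-linearly; this may dilute the Hypothesis 1 BOLD results

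*Combined protocol and SAP*

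**What the plan says.** All of this is in the combined protocol and SAP.

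- **BOLD.** Under MRI Analysis: "Functional data will be linearly registered to stereotaxic MNI space and co-registered with anatomic data for each participant".
- **Structural images.** In the same section: "Structural data (T1 and DTI) will be linearly registered to the standard MNI152 T1 2mm brain".
- **Perfusion.** Under Arterial Spin Labeling there are two steps. First, "These PASL images will then be linearly registered to each subject's T1 structural image". The processed maps are "then transferred to MNI space using non-linear registration in FSL".
- **Targets.** Under Crossover Design, at one visit "they will receive LIFUP sonication to the right amygdala, and at the other, they will receive sonication to the left entorhinal cortex".
- **Population.** "Participants will consist of 21 adults aged 35-90".
- **Anatomy available.** Under MRI Data Acquisition: "We will collect T1, T2, hi-res hippocampal T2, and diffusion-weighted structural images for each participant".

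Hypotheses 1a and 1b each predict both a BOLD change and a perfusion change in the amygdala and the entorhinal cortex. The Stimulation-related fMRI Analysis averages BOLD in the targeted and the control region and also runs a whole-brain, seed-based PPI. The RS-fMRI section uses ICA with dual regression. BOLD data are smoothed at 8 mm FWHM.

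The plan does not say where the ROI masks come from, in which space BOLD is extracted, or how registration is checked.

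**The concern.** A linear transform to a template corrects position, overall size and orientation. It cannot follow local differences in shape. In a sample spanning 35 to 90 years, such differences around the medial temporal lobe are to be expected, and both targets are small. The plan accepts a non-linear step for perfusion but not for BOLD, in the same people and for the same two regions.

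At stake is how well the BOLD part of Hypothesis 1 is measured. Where a participant's target does not line up with the template, the group analysis averages target tissue with its neighbours. The stimulation effect shrinks, and it becomes harder to tell a response in the sonicated region from none elsewhere. Hypotheses 1a and 1b depend on that distinction, because each says the change will be absent when the other region is sonicated. With 21 participants there is little reason to give signal away.

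**Working it through.** **No figure to reproduce.** The documents state no registration error, ROI size or power calculation bearing on this point. The check has two parts: a comparison of the text, and an illustration on stated assumptions.

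**1. The routes side by side**

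| Data | Route to MNI | Section |
|---|---|---|
| BOLD | linear; also co-registered to own anatomy | MRI Analysis |
| T1, DTI | linear | MRI Analysis |
| Perfusion | linear to own T1, then non-linear in FSL | Arterial Spin Labeling |

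**2. Which BOLD analyses depend on the MNI step**

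- *Whole-brain PPI.* Group inference across participants needs a common space. Linear MNI is the only one stated for functional data.
- *Dual regression.* The same holds for comparing resting-state networks across participants.
- *ROI means (on versus off).* These depend on the MNI step only if the masks are in MNI space, which is not stated.
- *Hypotheses 2 and 3, behavioural tests.* They use no registered image.

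**3. How much signal a residual shift costs**

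From the plan: FWHM = 8 mm, so σ = 8/2.3548 = 3.40 mm. Assumed: the signal is confined to a thin ribbon of thickness T = 4 mm (range 3-5 mm), and the ROI is displaced by d = 1, 2 or 3 mm across that thickness.

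Smoothed signal at position x: s(x) = Φ((x + T/2)/σ) − Φ((x − T/2)/σ).

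ROI mean at displacement d: M(d) = (1/T) ∫ s(x) dx, from d − T/2 to d + T/2.

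Retained fraction: R(d) = M(d)/M(0).

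For T = 4 mm, M(0) = 0.422:

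| d | M(d) | R(d) | Plain overlap 1 − d/T |
|---|---|---|---|
| 1 mm | 0.408 | 0.408/0.422 = 97% | 75% |
| 2 mm | 0.367 | 0.367/0.422 = 87% | 50% |
| 3 mm | 0.309 | 0.309/0.422 = 73% | 25% |

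Gain from cutting the error from 3 mm to 1 mm: 0.408/0.309 = 1.32.

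Sensitivity to the assumed shape, by the same method:

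- T = 3 mm: 96%, 86%, 71%; gain 0.319/0.235 = 1.36.
- T = 5 mm: 97%, 88%, 76%; gain 0.485/0.378 = 1.28.
- Sphere of 15 mm diameter (a compact target, computed numerically on a grid): 99%, 95%, 89%; gain 0.988/0.893 = 1.11.

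The loss is small at 1 mm, noticeable for a thin target at 3 mm, and larger for the thin shape than for the compact one.

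**4. What smoothing does on its own**

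M(0) = 0.422 means that, even with perfect alignment, the 8 mm kernel leaves only about 42% of a 4 mm ribbon's own signal in its ROI mean. In this model the kernel costs more than any of the three shifts.

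**The case against.** The strongest reply is that the plan never says BOLD is extracted with MNI masks. Functional data are also co-registered to each participant's anatomy, a high-resolution hippocampal T2 is collected, and the beam focus is located on the participant's own T1. Native-space ROI means are compatible with all of that and would not depend on the MNI step. This stands for the ROI means. It does not cover the whole-brain PPI or the dual regression, which need a common space.

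Four stronger readings are tempting, and the documents do not support them.

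- *The ROIs will be misplaced, most of all in the oldest participants.* This presumes MNI masks, and the documents give no registration error and no age gradient in it. Misalignment is a possibility, not a finding.
- *Better registration would triple the usable signal in a thin target.* That is plain geometric overlap for one thickness (75% against 25%). It ignores the planned smoothing, with which the gain is about 1.3-fold.
- *The comparison of BOLD with perfusion is broken.* No such comparison is planned. BOLD is tested on versus off within each ROI, and perfusion change is tested between sonication targets. Neither feeds the other.
- *The warp for BOLD already exists.* That the perfusion step uses a T1-to-MNI warp is the natural reading, but the plan does not say which image drives it, and elsewhere it registers T1 linearly.

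It is also fair to say that the on/off and pre/post contrasts are within participant, so a fixed offset mainly dilutes an effect and does not create one. Smoothing also limits localisation whichever registration is used. Both points limit the size of the problem. Neither is a reason to keep the weaker method for BOLD when the plan uses the better one for perfusion.

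**Conclusion.** The concern holds in a limited form. The plan states a linear route to MNI for BOLD and a non-linear one for perfusion, without a reason, for claims about the same two small regions. Group-level BOLD analyses may therefore be less well aligned than the perfusion maps, and so may ROI means if MNI masks are used. The consequence is diluted effects and weaker regional specificity within Hypotheses 1a and 1b.

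The size is modest: for a thin target, a loss of about 3% to 27% of ROI-mean signal over 1 to 3 mm of residual error, and about 1% to 11% for a 15 mm sphere. These figures rest on assumed errors and shapes, on signal confined to the target, and on the planned 8 mm kernel. They illustrate ROI means and are not estimates for this trial. The change is worth making because it is cheap and the plan already uses non-linear registration, not because the present choice would invalidate the results.

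**What to change.** In MRI Analysis, replace the linear step for functional data with this: each participant's BOLD images are co-registered to their own T1 and taken to MNI by a non-linear T1-to-MNI warp. Say in Arterial Spin Labeling that the same warp carries the perfusion maps, and bring the sentence on T1 registration into line.

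For ROI measures, name the mask source and extraction space, and use the same masks for BOLD and perfusion. These can be template masks applied through the common warp, or native-space masks drawn on each participant's T1 and high-resolution T2. Native masks alone would not serve the PPI and dual regression, so the warp is needed in either case. Add a visual check of each registration, ideally done without knowledge of the sonication condition, and a rule for failures.

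The cost is a little extra processing and visual checking of the warps in 21 participants. No new data are needed. A non-linear warp will not undo the blurring from the 8 mm kernel, so it should not be presented as securing localisation by itself.
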